### **13.7 Publications and Clinical Study Report**

#### **13.7.1 Publication of Study Results**

Vertex is committed to reporting the design and results of all clinical studies in a complete, accurate, balanced, transparent, and timely manner, consistent with Good Publication Practices (GPP3).

**Publication Planning:** Vertex staff along with the lead principal investigators, the steering committee, and/or the publication committee will work together to develop a publication plan.

**Authorship:** Authorship of publications will be determined based on the Recommendations for Conduct, Reporting, Editing, and Publication of Scholarly Work in Medical Journals, which states that authorship should be based on the following 4 criteria:

1. Substantial contributions to conception and design, acquisition of data, or analysis and interpretation of data;
2. Drafting of the article or revising it critically for important intellectual content;
3. Final approval of the version to be published; and
4. Agreement to be accountable for all aspects of the work in ensuring that questions related to the accuracy or integrity of any part of the work are appropriately investigated and resolved.

All authors must meet conditions 1, 2, 3, and 4. All persons designated as authors should qualify for authorship, and all those who qualify should be listed. Contributions such as medical writing, enrollment of subjects, acquisition of funding, collection of data, or general supervision of the research group, alone, do not justify authorship.

**Contributors:** Contributors who meet fewer than all 4 of International Committee of Medical Journal Editors (ICMJE) criteria for authorship will not be listed as authors, but their

contribution will be acknowledged and specified either as a group (e.g., “study investigators”) or individually (e.g., “served as scientific advisor”).

**Publication Review:** As required by a separate clinical study agreement, Vertex must have the opportunity to review all publications, including any manuscripts, abstracts, oral/slide presentations, and book chapters regarding this study before submission to congresses or journals for consideration.

### **13.7.2 Clinical Study Report**

A CSR, written in accordance with the ICH E3 Guideline, will be submitted in accordance with local regulations.

3 MODIFICATIONS

3.1 Modifications to the Approved Clinical Study Protocol

Not Applicable.

3.2 Modifications to the Approved Statistical Analysis Plan

Not Applicable. This is the 1st version of Statistical Analysis Plan.

4 INTRODUCTION

This statistical analysis plan (SAP) is based on the most recent approved clinical study protocol (CSP), the most recent approved electronic case report form (eCRF), and the most recent approved eCRF completion guidelines.

This SAP (Methods) documents the planned statistical analyses of efficacy and safety endpoints defined in the VX18-445-109 study protocol. It also documents analyses for additional efficacy and safety variables not specified in the protocol, which will provide supportive information for the scientific understanding of the drug entity.

The Vertex Biometrics Department will perform the statistical analysis of efficacy and safety data; SAS (Version 9.4 or higher) will be used to generate all statistical outputs (tables, figures, listings, and datasets). The SAP will be finalized and approved prior to the clinical database lock and treatment unblinding for the study. Any revisions to the approved SAP will be documented and approved in a SAP amendment prior to the clinical database lock and treatment unblinding. Any changes made to the SAP (Methods) after the clinical database lock has occurred will be documented in the clinical study report for this study.

5 STUDY OBJECTIVES

5.1 Primary Objective

To evaluate the efficacy of (ELX, VX-445)/TEZ/IVA in CF subjects, homozygous for *F508del* (F/F).

5.2 Secondary Objectives

- To evaluate the safety of ELX/TEZ/IVA
- To evaluate the pharmacodynamics (PD) of ELX/TEZ/IVA

6 STUDY ENDPOINTS

6.1 Efficacy and Pharmacodynamic Endpoints

6.1.1 Primary Endpoint

- Absolute change in CF Questionnaire-Revised (CFQ-R) respiratory domain score from baseline through Week 24

6.1.2 Key Secondary Endpoint

- Absolute change in percent predicted forced expiratory volume in 1 second (ppFEV₁) from baseline through Week 24

6.2 Secondary Endpoints

- Absolute change in sweat chloride (SwCl) from baseline through Week 24
- Safety and tolerability assessments based on adverse events (AEs), clinical laboratory values, ECGs, vital signs, and pulse oximetry

7 STUDY DESIGN

7.1 Overall Design

This is a Phase 3b, randomized, double-blind, active-controlled, parallel-group, multicenter study. A schematic of the study design is shown in [Figure 7-1](#).

[figure not shown]
In the TEZ/IVA Run-in Period, all subjects will receive TEZ 100 mg once daily (qd)/IVA 150 mg every 12 hours (q12h). After completing the TEZ/IVA Run-in Period, subjects will be randomized (1:1) to the ELX/TEZ/IVA group or TEZ/IVA group for the Treatment Period. Randomization will be stratified by ppFEV₁ determined during the TEZ/IVA Run-in Period (Day -14 assessment; <70 versus ≥70), age at the Screening Visit (<18 versus ≥18 years of age), and whether the subject is receiving CFTR modulator treatment at the Screening Visit (yes versus no). If the Day -14 ppFEV₁ value is not valid or not available, the most recent available ppFEV₁ value will be used for stratification.

The dosages for the Treatment Period are shown in [Table 7-1](#).

Table 7-1 Treatment Period Arms and Dosages

Treatment Arm	ELX Dosage	TEZ Dosage	IVA Dosage
ELX/TEZ/IVA	200 mg qd	100 mg qd	150 mg q12h
TEZ/IVA	0 mg	100 mg qd	150 mg q12h

IVA: ivacaftor; q12h: every 12 hours; qd: once daily; TEZ: tezacaftor

7.2 Sample Size and Power

The primary efficacy endpoint is the absolute change in CFQ-R respiratory domain score from baseline through Week 24. The primary null hypothesis to be tested is that the mean absolute change in CFQ-R respiratory domain score from baseline is the same for the 2 treatment groups, ELX/TEZ/IVA and TEZ/IVA. The null hypothesis will be tested at a 2-sided significance level of 0.05.

Assuming a within-group SD of 18 and a treatment difference of 10 between ELX/TEZ/IVA and TEZ/IVA, a sample size of 71 subjects completing the Treatment Period in each group for a total of 142 subjects will have approximately 90% power for the CFQ-R respiratory domain score hypothesis testing, based on a 2-sample *t*-test at a significance level of 0.05 (2-sided). Assuming a 10% dropout rate, approximately 158 subjects will be enrolled.

The key secondary endpoint is the absolute change in ppFEV₁ from baseline through Week 24. Assuming a within-group SD of 7 percentage points and a treatment difference of 5 between ELX/TEZ/IVA and TEZ/IVA, a sample size of 71 subjects completing the Treatment Period in each group for a total of 142 subjects will have approximately 98% power for the ppFEV₁ hypothesis testing, based on a 2-sample *t*-test at a significant level of 0.05 (2-sided).

All power calculations were based on EAST software Version 6.4.

7.3 Randomization

Randomization will be stratified by ppFEV₁ determined during the TEZ/IVA Run-in Period (Day -14 assessment; <70 versus ≥70), age at the Screening Visit (<18 versus ≥18 years of age), and whether the subject is receiving CFTR modulator treatment at the Screening Visit (yes versus no). If the Day -14 ppFEV₁ value is not valid or not available, the most recent available ppFEV₁ value will be used for stratification.

7.4 Blinding and Unblinding

Refer to the CSP Section 10.7 for details.

8 ANALYSIS SETS

The following analysis sets are defined: All Subjects Set, Full Analysis Set (FAS), Safety Set for the Run-in Period and Safety Set for the Treatment Period.

8.1 All Subjects Set

The **All Subjects Set** will include all subjects who are randomized or receive at least 1 dose of study drug (during either Run-in or Treatment Period). This analysis set will be used for all individual subject data listings and disposition summary tables, unless otherwise specified.

8.2 Full Analysis Set

The **Full Analysis Set** (FAS) will include all randomized subjects who carry the intended *CFTR* allele mutation and receive at least 1 dose of study drug in the Treatment Period. The FAS will be used to summarize subject demographics and baseline characteristics, and for all efficacy analyses in which subjects will be analyzed according to their randomized treatment group, unless otherwise specified.

8.3 Safety Set

The **Safety Set for the Run-in Period** will include all subjects who receive at least 1 dose of TEZ/IVA in the Run-in Period. This safety set will be used for all safety analyses during the Run-in Period, and for individual subject data listings, unless otherwise specified.

The **Safety Set for the Treatment Period** will include all subjects who receive at least 1 dose of study drug in the Treatment Period. This safety set will be used for all safety analyses during the Treatment Period in which subjects will be analyzed according to the treatment they receive, unless otherwise specified.

9 STATISTICAL ANALYSIS

9.1 General Considerations

Continuous variables will be summarized using the following descriptive summary statistics: the number of subjects (n), mean, SD, median, minimum value (min), and maximum value (max).

Categorical variables will be summarized using counts and percentages.

Baseline value, unless otherwise specified, will be defined as the most recent non-missing measurement (scheduled or unscheduled) collected before the first dose of study drug in the Treatment Period (i.e., the Day 1 Visit). For ECG, baseline will be defined as the most recent pretreatment measurement (or the average of triplicate measurements, if the most recent pretreatment measurement is obtained in triplicate) before the first dose of study drug in the Treatment Period (i.e., the Day 1 Visit).

Absolute change from baseline will be calculated as post-baseline value – baseline value.

Relative change from baseline will be calculated as (post-baseline value – baseline value)/baseline value.

The **Treatment-emergent (TE) Period for the Run-in Period** will be from the first dose of study drug in the Run-in Period to (1) the first dose of study drug in the Treatment Period for subjects who complete the Run-in Period and continue to the Treatment Period, or (2) 28 days after the last dose date of study drug in the Run-in Period or date of completion of study participation, whichever occurs first, for subjects who do not continue to the Treatment Period (e.g., subjects who do not meet the conditions to enter the Treatment Period).

The **TE Period for the Treatment Period** will include the time from the first dose date of study drug in the Treatment Period (ELX/TEZ/IVA or placebo + TEZ/IVA) to 28 days after the last dose of the study drug or to the date of completion of study participation, whichever occurs first.

Unscheduled visits: Unscheduled visit measurements will be included in analysis as follows:

- 1) In scheduled visit windows per specified visit windowing rules
- 2) In the derivation of baseline and last on-treatment measurements
- 3) In the derivation of maximum and minimum values during TE period, and maximum and minimum change from baseline values during TE period for safety analyses
- 4) In individual subject data listings as appropriate

Visit windowing rules: The analysis visit windows for protocol-defined visits are provided in [Appendix A](#).

Incomplete/missing data will not be imputed, unless specified otherwise.

Outliers: No formal statistical analyses will be performed to detect or remedy the presence of statistical outliers, unless specified otherwise.

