#### **9.1.2 Tezacaftor/Ivacaftor Run-in Period**

The TEZ/IVA Run-in Period has a 4-week duration and is designed to establish a reliable on-treatment (TEZ/IVA) baseline for the Treatment Period. The first dose of open-label TEZ/IVA will be administered at the Day -28 Visit. The last dose of open-label TEZ/IVA will be administered in the evening on Day -1 (1 day before the Day 1 Visit).

The Day -14 spirometry assessment will be used for stratification of randomization to the Treatment Period (Section 9.2).

Subjects who prematurely discontinue study drug treatment during the TEZ/IVA Run-in Period will not be randomized or participate in the Treatment Period (Section 9.1.5.1).

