### **9.3 Rationale for Study Elements**

#### **9.3.1 Study Design**

A randomized, double-blind, controlled study design was selected to assess the effects of VX-445/TEZ/IVA while avoiding observer bias. TEZ/IVA is considered an appropriate active control since TEZ/IVA (Symdeko/Symkevi) is approved to treat CF in this patient population.

A 4-week TEZ/IVA Run-in Period was incorporated into this study to establish a reliable on-treatment (TEZ/IVA) baseline for comparison during the Treatment Period.

The study will have a 24-week duration to allow for the collection of controlled efficacy and safety data.

The extent of response to CFTR modulator treatment may depend on the subject's ppFEV1 value (an index of disease severity) before the start of randomized study drug dosing. Some subjects in this study may be receiving treatment with LUM/IVA or TEZ/IVA at screening, while some subjects may not be receiving treatment with CFTR modulators. Therefore, randomization will be stratified by previous CFTR modulator use and ppFEV1 value determined during the TEZ/IVA Run-in Period after at least 13 days of treatment with TEZ/IVA (Day -14 assessment). Randomization will also be stratified by age at screening. This will ensure a balanced evaluation of adult and adolescent subjects.

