## 12.3 Statistical Analysis

### 12.3.1 General Considerations

**Continuous variables** will be summarized using the following descriptive summary statistics: the number of subjects (n), mean, SD, median, minimum value (min), and maximum value (max).

**Categorical variables** will be summarized using counts and percentages.

The **baseline value**, unless otherwise specified, will be defined as the most recent non-missing measurement (scheduled or unscheduled) collected before the first dose of study drug in the Treatment Period (i.e., the Day 1 Visit). For ECG, baseline will be defined as the most recent pretreatment measurement (or the average of triplicate measurements, if the most recent pretreatment measurement is obtained in triplicate) before the first dose of study drug in the Treatment Period (i.e., the Day 1 Visit).

**Absolute change** from baseline will be calculated as post-baseline value – baseline value.

The **Treatment-emergent (TE) Period for the Run-in Period** will be from the first dose of study drug in the Run-in Period to (1) the first dose of study drug in the Treatment Period for subjects who complete the Run-in Period and continue to the Treatment Period, or (2) 28 days

after the last dose date of study drug in the Run-in Period for subjects who do not continue to the Treatment Period (e.g., subjects who do not meet the conditions to enter the Treatment Period).

The **TE Period for the Treatment Period** will include the time from the first dose date of study drug in the Treatment Period (VX-445/TEZ/IVA or placebo + TEZ/IVA) to 28 days after the last dose of the study drug or to the completion of study participation date (as defined in Section 9.1.7), whichever occurs first.

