9.3.1 Analysis of Primary Efficacy Variable

9.3.1.1 Definition of Variable

The primary efficacy variable is the absolute change in CFQ-R respiratory domain (RD) score from baseline through Week 24.

Cystic Fibrosis Questionnaire-Revised (CFQ-R): The CFQ-R^{3,4,5} is a validated CF-specific instrument that measures quality-of-life domains. This study utilizes three different versions of CFQ-R:

- CFQ-R for Children ages 12 and 13
- CFQ-R for Adolescents and Adults (subjects 14 years and older)
- CFQ-R for Parents/Caregivers (subjects 13 years and younger)

In all three versions, specific question belonging to a domain is scored 1, 2, 3, or 4. The CFQ-R domain score, e.g., physical domain score or respiratory domain score, is defined as a scaled score as follows:

Scaled score for a domain = $100 \times (\text{mean}(\text{scores of all questions in the domain}) - 1)/3$, where the score from a negatively phrased question is first reversed, i.e., reversed score = $5 - \text{actual score}$, so that 1 always represents the worst condition and 4 the best condition. The (scaled) domain score ranges from 0 (worst condition) to 100 (best condition). The scaled score for a specific domain will not be calculated if more than half of the questions in the domain have missing scores.

The (scaled) domain score from the CFQ-R for Children ages 12 and 13 and for Adolescent and Adults will be pooled for the analysis purpose.

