12 LIST OF APPENDICES

Appendix A: Analysis Visit Windows for Safety and Efficacy Assessment

Table 12-1 Analysis Visit Windows for Safety and Efficacy Assessments			
Assessment	Visit¹	Target Study Day	Analysis Visit Window (in study days)^{2,3,4,5}
Safety Assessment			
Serum Chemistry Hematology	Day 1 (Baseline)	1	≤1 Pre-dose
	Day 15	15	[1, 22]
	Week 4	29	(22, 43]
	Week 8	57	(43, 85]
	Week 16	113	(85, 141]
	Week 24	169	(141, 183]
	Safety Follow-up	Not applicable	Use nominal visit
Standard 12-lead ECG	Day 1 (Baseline)	1	≤1 Pre-dose
	Week 8	57	[1, 113]
	Week 24	169	(113, 183]
	Safety Follow-up	Not applicable	Use nominal visit
Vital signs and pulse oximetry (excluding BMI, Weight, Height and their Z-scores)	Day 1 (Baseline)	1	≤1
	Day 15	15	[1, 22]
	Week 4	29	(22, 43]
	Week 8	57	(43, 85]
	Week 16	113	(85, 141]
	Week 24	169	(141, 183]
	Safety Follow-up	Not applicable	Use nominal visit
Coagulation	Day 1 (Baseline)	1	≤1 Pre-dose
	Week 24	169	[1, 183]
	Safety Follow-up	Not applicable	Use nominal visit
BMI, Weight, Height and their Z-scores	Day 1 (Baseline)	1	≤1
	Day 15	15	(1, 22]
	Week 4	29	(22, 43]
	Week 8	57	(43, 85]
	Week 16	113	(85, 141]
	Week 24	169	(141, 183]
	Safety Follow-up	Not applicable	>183
Efficacy Assessment and Pharmacodynamic Assessment			
Spirometry	Day 1 (Baseline)	1	≤1 Pre-dose
	Day 15	15	(1, 22]
	Week 4	29	(22, 43]
	Week 8	57	(43, 85]
	Week 16	113	(85, 141]
	Week 24	169	(141, 183]
	Safety Follow-up	Not applicable	>183
Sweat Chloride	Day 1 (Baseline)	1	≤1 Pre-dose
	Week 4	29	(1, 43]
	Week 8	57	(43, 113]
	Week 24	169	(113, 183]

Table 12-1 Analysis Visit Windows for Safety and Efficacy Assessments			
Assessment	Visit¹	Target Study Day	Analysis Visit Window (in study days)^{2, 3, 4, 5}
CFQ-R	Day 1 (Baseline)	1	≤1
	Week 4	29	(1, 43]
	Week 8	57	(43, 85]
	Week 16	113	(85, 141]
	Week 24	169	(141, 183]
	Safety Follow-up	Not applicable	>183

Notes:

¹ Visit name for analysis purpose is used to report data in tables and figures.

² The analysis visit windows will be applied using the following rules for both scheduled and unscheduled visits:

- If no numerical measurement is available within a visit window, the measurement will be considered missing for the visit.
- If there is more than 1 numerical measurement available within a visit window, use the following rules:
 - The measurement closest to the target day will be used; or
 - If there are multiple measurements with the same distance from the target day, the latest measurement will be used.

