
If the first dose date is missing, use Day 1 visit date to impute.
 
If the last dose date is missing or partial date is reported, the last dose date will be imputed based on, in descending order priority, the Early Treatment Termination (ETT) visit date, last visit date before the Safety Follow-up, or the last study drug administration date from EX SDTM domain, as appropriate. The imputation algorithm will ensure the imputed last dose date does not exceed the study participation end date.
 
4. Sweat Chloride:
 
Non-missing sweat chloride concentrations from the left arm and right arm with assessment end date/time for a given arm up to 30 minutes after first dose time in treatment period will be considered for baseline.
 
5. Electrocardiogram:
 
Baseline is defined as the most recent pretreatment measurement before the first dose of study drug in the Treatment Period. If multiple ECG measurements are obtained on the same calendar day during the TE period,
 
 ○ For summary purpose, the calculated average ECG will be used as the ECG value on that day; ○ For threshold analysis purpose, all reported ECG values will be used. 			

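### Does letting the CFQ-R baseline fall back to the Screening score, when Day 1 cannot be scored, undermine the primary analysis?

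*SAP*

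**What the plan says.** In SAP 9.1 the baseline value is "defined as the most recent non-missing measurement (scheduled or unscheduled) collected before the first dose of study drug in the Treatment Period", and protocol 12.3.1 gives the same rule. In SAP Appendix A, Table 12-1, the CFQ-R baseline window is study day 1 or earlier, with no lower limit.

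Protocol Table 3-1 schedules a CFQ-R at Screening (Day -56 to Day -29). In Table 3-2 the next one is at Day 1, with none at Day -28 or Day -14. Spirometry and sweat chloride do have a Day -14 assessment.

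On scoring, SAP 9.3.1.1 says: "The scaled score for a specific domain will not be calculated if more than half of the questions in the domain have missing scores".

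Protocol 9.1.2 says that the run-in "is designed to establish a reliable on-treatment (TEZ/IVA) baseline for the Treatment Period". Protocol 9.3.1 notes that some subjects "may be receiving treatment with LUM/IVA or TEZ/IVA at screening, while some subjects may not be receiving treatment with CFTR modulators".

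The primary analysis (SAP 9.3.1.2) is an MMRM on change from baseline. Its covariates are baseline ppFEV1, age group and modulator use at Screening. The primary result is the treatment difference averaged over Weeks 4, 8, 16 and 24.

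**The concern.** The design spends four weeks putting every subject on TEZ/IVA so that change is measured from an on-TEZ/IVA value. For the primary endpoint, only the Day 1 questionnaire delivers that value on schedule. If it cannot be scored, the last available score is normally the one from Screening. For a subject then on LUM/IVA or no modulator, that is not an on-TEZ/IVA baseline, and the change score absorbs whatever happened during the run-in. The interval is also longer: 29 to 56 days before Day 1, or up to 70 with the two-week extension in protocol 9.1.1.3.

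SAP 9.2.2 summarises baseline CFQ-R only as a continuous variable. The additional analyses in SAP 9.3.1.2 deal with COVID-19 timing and with home versus clinic data, and the subgroups in 9.3.1.3 are unrelated to the source of baseline. A reader could therefore not tell from the planned tables whether the fallback was used. At stake would be the meaning of the within-arm changes and, if the fallback distorted the comparison, the primary result itself.

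**Working it through.** **The plan's own figure.** Protocol 12.1 gives SD 18, difference 10, 71 completers per arm and a two-sided 0.05 level.
- Standard error of the difference: 18 × √(2/71) = 3.02.
- Two-sample t-test power (noncentral t): 90.8%, which reproduces the stated figure of about 90%.
- Enrolment: 142 / 0.90 = 157.8, so 158, as stated.

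**Bias in the treatment difference.** Write the change as Y − B, where B is the Day 1 score or, failing that, the Screening score.
- Both scores are taken before the first randomised dose.
- Randomisation may take place on Day -1 or Day 1 (protocol 9.1.3), so a Day 1 questionnaire may follow assignment. Assignment is blinded, however, and no randomised drug has been taken, so neither the score nor its being missing can depend on the arm.
- Hence E(B) is equal in the two arms under either source, and the expected bias in the difference is 0.

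**Within-arm shift.** Let f be the share of subjects affected, u the share of those not on TEZ/IVA at Screening, and d the run-in change in points. Shift = f × u × d. The documents give none of the three. Assumed ranges: f = 1-5% (about 2-8 of 158), u = 0-100%, d = 3-8 points in either direction.

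| f | u | d | Shift (points) |
|---|---|---|---|
| any | 0 | any | 0 |
| 0.02 | 0.5 | 3 | 0.03 |
| 0.02 | 0.5 | 8 | 0.08 |
| 0.05 | 1 | 8 | 0.40 |

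The maximum needs all three worst cases together and is 0.40/10 = 4% of the design difference. It applies equally to both arms in expectation, so it cancels in the comparison.

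**Chance imbalance between arms.** The added SD of the difference is d × √(2f(1−f)/n). With d = 8, f = 0.05 and n = 71 it is 8 × √(0.095/71) = 0.29 points; with the 79 randomised per arm it is 0.28. Combined with 3.02, the standard error becomes √(3.02² + 0.29²) = 3.03.

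**Power with these subjects kept in.** Suppose 5% are affected, their SD is 22 instead of 18, and their mean is shifted by 8 points. The variance is 0.95 × 324 + 0.05 × 484 + 0.05 × 0.95 × 64 = 335.0, the SD is 18.3 and power is 89.8%. With no extra spread or shift it is 90.8%. A harsher case, 10% affected with a 10-point shift and SD 18 otherwise, gives SD √(324 + 0.10 × 0.90 × 100) = 18.25 and power 90.0%.

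**Power if these subjects were left out.** Dropping 5% leaves 67.45 per arm and power 89.3%, slightly below the 89.8-90.8% from keeping them.

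**The case for a change.** The strongest case for the concern is that the CFQ-R is the primary endpoint and yet the one main measure without a scheduled run-in value to fall back on. Appendix A sets out specific baseline handling for sweat chloride and ECG but none for the CFQ-R. LS means by arm are plotted and changes are summarised by visit, so within-arm changes will be read. A count by arm would cost one table row, and specifying it before database lock would avoid a post hoc choice.

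The schedule is as described, and the fallback can occur. The rest carries little weight:

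- The contrast with the other measures does not hold. The sweat chloride provision says that concentrations with an end time "up to 30 minutes after first dose time in treatment period will be considered for baseline", which extends the window forward. The ECG provision restates the most-recent rule and handles repeat readings. Neither limits how old a baseline may be, so the CFQ-R lacks no safeguard that they have.
- Appendix A also says: "If no numerical measurement is available within a visit window, the measurement will be considered missing for the visit". That does not mark a missing Day 1 score as a missing baseline, because a Screening score lies inside the CFQ-R baseline window. The text is consistent on this.
- The plan already makes the case unlikely. Day 1 is a clinic visit, the CFQ-R precedes every other assessment there, and the domain is scored with up to half its items missing. Unscheduled questionnaires also count towards baseline.
- Modulator use at Screening (yes/no) is a stratification factor, a covariate and a subgroup. It does not separate LUM/IVA from TEZ/IVA, but it covers the no-modulator group.
- COVID-19 impacted visits are listed (SAP 9.4.8). Deviations that affect completeness or reliability can be classed as important and summarised by arm (SAP 9.2.7). Neither is a count by baseline source, but a missed Day 1 assessment need not go unseen.

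What stands is that a count by source of baseline would be informative description. The available text plans none, although a redaction in protocol 12.3.3.1, where additional analyses are mentioned, prevents certainty. An unplanned descriptive row is a preference and does not show an error.

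**Conclusion.** The concern does not hold. The plan says in advance what happens when Day 1 is missing, says it identically in protocol and SAP, and keeps the subject in the analysis. Following the rule gives a sound primary result: zero expected bias in the treatment difference, a standard error that moves from 3.02 to at most about 3.03 through chance imbalance, and power of 89.8-90.8%. The only systematic effect is on within-arm mean changes, at most 0.40 points and 0.03-0.08 in a middle case.

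The sizes rest on assumed values for the share affected (1-5%), the share of those not on TEZ/IVA at Screening (0-100%) and the run-in change (3-8 points). Nothing in the documents shows that any subject will be affected. The absence of bias does not depend on those values. It rests on randomisation, blinding and a baseline taken before randomised dosing. No change to the baseline rule, the FAS or the primary model is needed.
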